Patients and/or surrogate decision maker who do not give consent to treatment will be asked to allow collection of data from their medical record for use as a control group. Patients or surrogate decision makers who cannot consent in person, will be consented in accordance to the KUMC remote consent guidelines.

Parameters to be collected:

General: Demographics, clinical symptoms, history of other medical conditions, routine blood work, and concomitant medications. Baseline characteristics will include age, sex, race, ethnicity and body mass index, Simplified Acute Physiology Score (SAPS) II, National Early Warning Signs (NEWS), Sequential Organ Failure Assessment (SOFA) and acute physiology and chronic health evaluation (APACHE) II. The APACHE II will be collected only for participants admitted in the ICU.

Physical examination: We will record vital signs such as highest and lowest temperatures (°C), highest respiratory rate, highest heart rate, lowest mean arterial pressure (mmHg), highest oxygen requirements and body mass index (BMI).

Confirmation of infection with SARS-CoV-2 by PCR testing by chart. Also, documentation of other infections if present.

Blood samples: We will collect laboratory values throughout the study (hemoglobin, platelet count, white blood cell count, lymphocyte count, liver enzymes, glucose, blood urea nitrogen, creatinine, creatine kinase, lactate, and arterial blood gas) and as indicated (LDH, ferritin, troponin), potassium and other values available in EMR. Store plasma at beginning and at the end of study for later analysis (possibly IL-6 etc.).

Nasopharyngeal swabs: We will collect nasopharyngeal swabs at study enrollment and end of study to determine SARS-CoV-2 viral load by quantitative PCR.

Radiographic imaging will be recorded upon presentation and subsequently thereafter as indicated.

Monitor for deteriorating acute respiratory failure and determine the indication the need for mechanical ventilation.

Study procedures (see schematic)

Day 0

- Labs collected for routine clinical care and the medical record will be reviewed to screen for eligibility. Assuring pre-menopausal women have a negative pregnancy test.
- Consenting participants who meet enrollment criteria will be started on losartan 25 mg once daily per mouth.
- Treatment group will have nasopharyngeal swab and research plasma collected for analysis.
- Control group will be followed only for data collection until study completion.

Day 1-2:

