- Monitor subject for safety and losartan stoppage criteria.
- For participants following inclusion criteria #5: Day 0 assessments should be performed on enrollment day as well as day 1 **or** day 2 based on first dose of SOC losartan administration.

Day 3:

- Dose escalation: On study day 3 if none of the parameters listed below are met the dose of losartan will be increased to 50 mg once daily.

Day 4 until study completion:

- Monitor subject for safety and losartan stoppage criteria.
- Treatment group will have nasopharyngeal swab and research plasma collected at end of study.

Stoppage criteria for losartan

- Hyperkalemia (persistent values >5.5 mM recorded on at least 2 readings).
- Worsening renal function (Cockcroft-Gault <30 mL/min/1.73 m²) or urinary output <20 mL/h.
- Skin rashes, palpitations or other moderate or severe adverse events (interference with usual daily activities) without clear explanation should warrant immediate cessation of treatment and notification of study personnel.
- Development of sustained hypotension defined as SBP <90 mmHg, DBP <60 mmHg recorded on at least two readings 30 min apart or use of norepinephrine >0.1 µg/kg/min.

[figure not shown]
- Any change in monitor lab parameters deemed significant and potentially related to study drug by the Investigator.

Dose de-escalation criteria

- Any change in monitoring parameter after dose increase from 25 mg to 50 mg that is considered significant by the investigator will trigger a decrease dose back to 25 mg
- If abnormal parameter is resolved and, in the opinion of the investigator, is unlikely to be related to losartan will increase dose back to 50 mg
- If de-escalation criteria is met after re challenging 50mg dose, the dose will be once more decreased to 25mg until the end of the study.

Criteria for resuming after stopping

- If stoppage criteria have resolved and reason for stoppage is felt to be unlikely or possibly related to losartan, discussion of resumption of losartan with medical monitor
- Dose resumption will start at 25 mg. If stopped at 25 mg → the dose will be continued for three days followed by increase to 50 mg if tolerated. If stopped at 50 mg, 25 mg will be started and escalated to 50 mg the day after if tolerated.

Control

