Since there is no information on the effects of losartan in human beings suffering from COVID-19, a statistical analysis based on efficacy is not possible. From a safety perspective, we would accept considering losartan equivalent or superior to the comparison group not receiving losartan (historical or no consent) if there is a $\pm 20\%$ difference in total AE/SAEs. Historical controls will be matched with study participants based on upon age, sex and disease severity in a 2:1 ratio for safety comparison. From a safety perspective, losartan's long track record as a safe medication is reassuring. See section on DSMB for further details on safety monitoring and analysis.

Confidentiality

All information provided by the subject to the investigators, and all information that is collected about the subjects by the investigators, shall be kept confidential to the extent that is provided by law. Computer data files will be stored and backup up to secure, HIPPA compliant, password protected computers and servers. Electronic data capture into REDCap system will be used. Access to these databases will be restricted to individuals associated with the study who require access to the data to perform their duties. These individuals will be named by the principal investigator prior to initiation of the clinical trial. The subject's actual identity cannot be ascertained exclusively from these data and the subject's name shall not be used in any publications. All investigators and staff involved in the research protocol will be bound by this agreement of confidentiality.

Adverse Event and Serious Adverse Event Documentation

Definition of an Adverse Event

For the purpose of this protocol, an AE will be defined as any untoward medical occurrence in a subject during the study listed under DMSB - Anticipated Adverse Events and Grading Scale section of this protocol as well as safety monitoring data listed on table 1 as well as stoppage criteria for losartan.

The event does not necessarily have a causal relationship with the treatment. AEs will be collected for both study groups, treatment and control from the time the ICF is signed until the subject completes study participation.

Definition of a Serious Adverse Event

An SAE is any AE that meets any of the following outcomes:

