AST, ALT, alkaline phosphatase	>ULN - 3.0 x ULN; monitor closely	Asymptomatic with AST, ALT, alk.P. >3.0 - 5.0 x ULN; >3 x ULN with the appearance of worsening of fatigue, nausea, vomiting, right upper quadrant pain or tenderness, fever, rash, or eosinophilia or bilirubin elevation; stop losartan, monitor	>5.0 - 20.0 x ULN; >5 x ULN for >2 weeks; stop losartan, monitor	>20.0 x ULN; stop losartan, monitor, other interventions	
CPK#	>ULN - 2.5 x ULN; monitor closely	>2.5 x ULN - 5 x ULN; stop losartan, monitor closely	>5 x ULN - 10 x ULN; stop losartan, monitor closely	>10 x ULN; stop losartan, monitor closely, possible admission with other abnormalities	

& Given that hyperkalemia occurs with patients on Losartan and there could be patients with renal dysfunction that falls just under the 1.5 mmol/L creatinine exclusion point, the DMC would recommend a modification to the reporting of abnormal results of serum potassium. We suggest that upon receipt of a level greater than 5.5 mM, the blood draw be repeated within 24 hours and that the PI for the study respond to the repeat level by either reassuring the patient that all is well or if the level is still rising discontinuing the study drug. Since there will be blood draws frequently during this study, we feel that continuing the study subject on study drug if the level returned to normal on repeat testing is safe, especially in the expected monitored setting.

Only done when clinically indicated

Pregnancy

Female subjects will be tested for pregnancy by hospital policy. If pregnant they will be excluded.

It is not expected that a female subject becomes pregnant while participating in the study. In the rare case this does occur, study drug must be stopped immediately and permanently discontinued. Losartan does not have effects on a fetus in the 1st trimester but could later on. The investigator must notify the DSMB and IRB within 24 hours of the site's knowledge of the subject's pregnancy and other agencies as by law. Pregnancy itself does not constitute an AE. Pregnancy test will be performed at all site visits.

Data monitoring plan will be implemented as follows:

- Safety monitoring will be done:
 - All SAEs attributable to study drug will be reported to the study investigator(s) and discussed with an internal safety and monitoring group of 5 experts consisting of an intensivist(s), infectious disease specialist(s), ethicist and biostatistician. These experts may not report to the PI directly.

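### Hypotension and CPK events enter the between-group AE total without a common data source or rule for losartan patients and controls

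*Combined protocol and SAP*

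**What the plan says.** All references are to the combined protocol and SAP.

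- **Sample size and Statistics** accepts losartan as equivalent or superior to the comparison group "if there is a $\pm 20\%$ difference in total AE/SAEs". It does not say whether the 20% is absolute or relative.
- **Definition of an Adverse Event** counts, besides the anticipated events, "safety monitoring data listed on table 1 as well as stoppage criteria for losartan".
- **Stoppage criteria for losartan** includes "Development of sustained hypotension defined as SBP <90 mmHg, DBP <60 mmHg recorded on at least two readings 30 min apart", with norepinephrine above 0.1 µg/kg/min as an alternative. Another criterion uses urinary output.
- **Parameters to be collected, Physical examination** opens with "We will record vital signs such as highest and lowest temperatures" and goes on to "highest heart rate, lowest mean arterial pressure (mmHg), highest oxygen requirements and body mass index (BMI". No systolic or diastolic pressure, reading time, norepinephrine dose or urine output is named.
- **Parameters to be collected, Blood samples** puts creatine kinase in the group collected throughout the study ("glucose, blood urea nitrogen, creatinine, creatine kinase, lactate, and arterial blood gas"), apart from a separate as-indicated group.
- **Table 1** labels its row CPK#. A note below the table reads "Only done when clinically indicated". The symbol before the note was lost in text extraction, so its link to CPK is inferred from the row label.
- **Table 1, hypotension rows** grade by vasopressor use, symptoms, intervention and organ damage. They contain no systolic or diastolic limit.

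**The concern.** The primary hypothesis is safety, and the one stated comparison is a difference in AE totals between a treated group and non-randomised controls. Such a comparison is fair only if an event has the same chance of being recorded in each group.

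For two event types the plan does not secure this. The named blood pressure variable does not match the stoppage-criterion definition of hypotension. That matters most for retrospective controls, whose events can come only from recorded data. For CPK, the plan does not settle whether everyone is tested or only those for whom a clinician orders the test. A difference in AE totals could then partly reflect how events were looked for.

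**Working it through.** **No plan figure to reproduce.** The 50 treated patients and the 2:1 control ratio are stated without alpha, power or an expected AE rate. The check is therefore on definitions, plus one illustration.

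**1. Can lowest mean arterial pressure (MAP) identify the criterion?**

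Formula (standard approximation): MAP = (SBP + 2 × DBP)/3. Assumed scan: SBP 60–180, DBP 30–120, pulse pressure 15–100 mmHg. The stoppage criterion joins its two limits with a comma, so both readings are tested. Exclusion criterion 6 uses *or* for the same limits.

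| Reading | MAP | Either limit (*or*) | Both limits (*and*) |
|---|---|---|---|
| 88/70 | (88+140)/3 = 76.0 | meets | no |
| 130/58 | (130+116)/3 = 82.0 | meets | no |
| 90/60 | (90+120)/3 = 70.0 | no | no |
| 95/60 | (95+120)/3 = 71.7 | no | no |
| 89/59 | (89+118)/3 = 69.0 | meets | meets |
| 90/30 | (90+60)/3 = 50.0 | meets | no |

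Over the whole scan:

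- *Or*: qualifying readings have MAP 40–92, non-qualifying 70–140. MAP from 70 to 92 is undecided.
- *And*: qualifying 40–69, non-qualifying 50–140. MAP from 50 to 69 is undecided.

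MAP settles the status of a single reading only outside these bands. One lowest value also cannot show that two readings 30 minutes apart were below the limits, and it carries no information on norepinephrine.

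**2. Does Table 1 supply the missing definition?** No. It has no pressure limit, so a pair of low readings counted under the stoppage criteria and a Table 1 hypotension grade are different events. The row for sedated, ventilated ICU participants needs a vasopressor dose, which the collection list does not name.

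**3. How does each group come to have an event?**

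| | Losartan patients | Consenting controls | Retrospective controls |
|---|---|---|---|
| Follow-up | Monitored against stoppage criteria (Study procedures) | Data capture only (Study procedures, Day 0) | Health-record query (Control) |
| AE collection starts | Consent form signed | Consent form signed | No consent form, so no start stated |

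**4. How much could CPK matter?** Illustration with assumed inputs: equal true rate p in both groups, all treated patients tested, a share f of controls tested, one event per patient at most.

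Spurious difference = p − p × f.

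- p = 20%, f = 50%: 0.20 − 0.10 = 10 points. In counts, 50 × 0.20 = 10 of 50 treated against 100 × 0.20 × 0.50 = 10 of 100 controls.
- Smallest case, p = 10%, f = 75%: 0.10 − 0.075 = 2.5 points.
- Largest case, p = 30%, f = 25%: 0.30 − 0.075 = 22.5 points.

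If the 20% tolerance is absolute, the largest case alone exceeds it. Neither p nor f is given in the documents.

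**The case against.** The strongest reply is that an unnamed field is not an absent one. The vital-sign list is illustrative, as its opening words show. The collection section also covers concomitant medications and other values in the electronic record. The Control section promises safety-criteria information on historical controls, and the AE definition says events are collected in both groups. Exact fields may sit in the REDCap forms, which are not part of these documents. All of this stands. A reader might infer that the planned data cannot produce the hypotension events; the documents do not support that. What remains is that nothing requires the same readings to be extracted, or the same rule applied, in both groups.

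A reader might also infer that the hypotension comparison must be biased against losartan because low blood pressure is its main expected effect. The plan says otherwise: it names fatigue and dizziness as most common, places hypotension among rare serious events, and expects little blood pressure effect at these doses. Hypotension is still an anticipated AE and a stoppage criterion, so it counts.

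On CPK, the plan describes rhabdomyolysis through clinical assessment of muscle pain, which fits testing on indication. Controls may include patients with exclusion criteria, who could be tested more often, so the direction is open. The two statements still conflict if the note belongs to CPK.

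Potassium is no comparable gap: the collection section lists it.

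**Conclusion.** The point holds as one of unaligned ascertainment. Lowest MAP, the only blood pressure item named, cannot reproduce the stoppage-criterion hypotension event under either reading of the comma; this rests on the standard MAP approximation and the scanned pressure ranges. The plan has two differing hypotension definitions, both counted as AEs, and groups that reach an event by different routes. CPK collection is stated two ways, provided the Table 1 note belongs to the CPK# row.

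No effect on the AE total is demonstrated. The 2.5 to 22.5 point range shows what unequal CPK testing could do under assumed rates and is not an estimate. The matter should be settled before the between-group comparison is run, because the correction is cheap and the comparison carries the trial's main conclusion.

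**What to change.** 1. In Parameters to be collected, for treated and control patients alike, name all time-stamped SBP and DBP readings, norepinephrine dose and recorded urine output, taken from the existing record. A summary field will not do. Suppose SBP is 88 at 10:00, 85 at 10:30 and 95 at 11:00, with DBP below 60 at the first two. Keeping the lowest reading and the next one gives 85 and 95 and misses the qualifying pair.
2. Derive the stoppage-criterion hypotension event by one program in both groups, and use that derived event in the between-group comparison. The sponsor should state whether the comma means *or* or *and*. Bedside-identified events in treated patients continue to be reported as safety data.
3. Reconcile the hypotension definitions in the stoppage criteria and Table 1, and say which events enter the total. No clinical threshold is proposed here.
4. Reconcile the Blood samples paragraph with the Table 1 note on CPK. If CPK stays indication-only, report it separately and leave it out of the between-group AE total.

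Cost: some extra data extraction and a few database fields, with no added patient procedure. If CPK stays indication-only, its comparison also sits outside the total. One limit remains: a common program equalises the rule but not how often pressure was measured, so the number of readings per patient-day should be shown by group.

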Thus, good evidence suggests that at least acute treatment with ARBs could ameliorate lung injury in COVID-19. We therefore propose to test losartan in a Phase I proof of concept and safety trial. The primary hypothesis to be tested is that losartan treatment is safe in the setting of acute SARS-CoV-2 infection. Secondarily, losartan can potentially reduce the length of respiratory failure due to SARS-CoV-2.

Significance

Importance of the problem: As outlined above, there is currently no data that supports specific treatment options for respiratory failure in COVID-19. There are active or soon to be active clinical trials that may show promise in this space such as blocking IL-6 with tocilizumab²⁰ or using hydroxychloroquine. None of these therapies are without side effects and alternative or additional approaches could lessen the burden of respiratory failure in this patient population.

Approach and Protocol

This is an open label, phase 1 clinical trial to evaluate the safety of losartan in respiratory failure due to COVID-19.

Clinical Trial setup:

Detailed inclusion and exclusion criteria are listed below. Briefly, 50 patients with COVID-19 and respiratory failure who meet criteria and agree to participation in the study will be placed on losartan 25 mg daily on study day 0. If parameters are met the dose of losartan will be increased to 50 mg on study day 3. Participants will continue losartan until they experience resolution of respiratory failure (normal oxygen levels on room air), are discharged from the hospital, meet stoppage criteria (detailed below) or complete 14 days of therapy.

Primary hypothesis and endpoint:

- Losartan is safe in acute respiratory failure due to SARS-CoV-2.

Secondary endpoints:

- Losartan reduces the number of days on supplemental oxygen in respiratory failure due to COVID-19
- Incidence of mechanical ventilation use
- Days on mechanical ventilation
- Incidence of non-invasive positive pressure ventilation or heated high flow nasal cannula use
- Days on non-invasive positive pressure ventilation or high flow nasal cannula
- Incidence of transfer to ICU from non-ICU hospital bed
- ICU length of stay (days)
- In-hospital mortality
- Hospital length of stay (days)
- Cumulative incidence of severe adverse events
- Cumulative incidence of adverse events
- Change from baseline in oxygenation

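### Adverse-event detection is not made equal between losartan patients and controls, yet safety is judged on total AE/SAE counts

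*Combined protocol and SAP*

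**What the plan says.** The Clinical Trial setup section states that "50 patients with COVID-19 and respiratory failure who meet criteria and agree to participation in the study will be placed on losartan". The primary hypothesis is safety. Under Sample size and Statistics, losartan is accepted as equivalent or superior "if there is a $\pm 20\%$ difference in total AE/SAEs", and "Historical controls will be matched with study participants based on upon age, sex and disease severity in a 2:1 ratio for safety comparison". Neither the scale of the 20% (relative or percentage points) nor the counting unit (patients, events or single results) is given.

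The Definition of an Adverse Event limits AEs to listed items, "as well as safety monitoring data listed on table 1 as well as stoppage criteria for losartan".

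Follow-up differs by group:

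- **Losartan patients.** Under Study procedures, Day 1-2 and again from Day 4, staff are told to "Monitor subject for safety and losartan stoppage criteria". Table 1 attaches closer follow-up or further investigation to many abnormal grades, next to the instruction to stop losartan. Its potassium footnote suggests that after a value above 5.5 mM "the blood draw be repeated within 24 hours", and it reasons from an expectation of frequent sampling: "Since there will be blood draws frequently during this study".
- **Controls.** Under Day 0, "Control group will be followed only for data collection until study completion". The Control section adds patients found retrospectively by querying the health record, who give no consent.

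**The concern.** A threshold crossing that nobody samples is never recorded as an AE. Seven of the ten rows of Table 1 are laboratory tests (hemoglobin, leukocytes, platelets, creatinine, potassium, the liver enzymes, CPK), so the count depends on how often blood is drawn and how closely results are pursued. The plan sets up protocol-driven surveillance in one group and chart abstraction in the other, then compares totals with no common counting rule.

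The stoppage criteria add an asymmetry that does not depend on testing. One of them is a laboratory change that the investigator considers significant and possibly due to study drug. Because stoppage criteria count as AEs, this is an AE category that an untreated patient cannot enter.

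At stake is the primary conclusion. With no drug effect, losartan could look worse because it was watched more closely. Equally, a true renal or potassium excess could be dismissed as an artefact of closer watching, and the planned data summary could not settle the question.

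**Working it through.** **Nothing to reproduce.** The documents give no test counts, no AE rates and no calculation behind the ±20%. The figures below show only how sensitive the comparison is. The values of s, r, p, m, the correlation and the potassium shares are assumptions. All calculations assume no drug effect.

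**1. Every abnormal result counted as an event.** Let s be the laboratory share of AEs among controls and r the ratio of tests per patient, losartan to control. The ratio of total AEs is 1 + s(r − 1). Setting it to 1.20 gives r = 1 + 0.20/s:

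| s | r needed for a ratio of 1.20 |
|---|---|
| 1.00 | 1.20 (20% more tests) |
| 0.75 | 1.27 |
| 0.50 | 1.40 (40% more tests) |
| 0.25 | 1.80 (80% more tests) |

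At r = 1 the ratio is 1 and there is no bias. At r below 1 the bias favours losartan.

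**2. Patients with any abnormal result, independent draws.** With chance p per draw and m draws, the probability is 1 − (1 − p)^m. Take p = 0.05:

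- 7 draws: 1 − 0.95^7 = 30.2%
- 10 draws: 1 − 0.95^10 = 40.1%, which is 10 points and a ratio of 1.33 against 7 draws
- 14 draws: 1 − 0.95^14 = 51.2%, which is 21 points and a ratio of 1.70 against 7 draws

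For p from 1% to 10%, 10 against 7 draws gives a relative excess of 25% to 41% (2.8 to 13.0 points). Doubling to 14 gives 48% to 93% (6.3 to 25.0 points).

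**3. The same, with correlated draws.** Serial results in one patient are not independent. A beta-binomial model with within-patient correlation ρ gives 1 − B(a, b + m)/B(a, b), where a = p(1 − ρ)/ρ and b = (1 − p)(1 − ρ)/ρ. At ρ = 0.5 and p = 0.05, so a = 0.05 and b = 0.95:

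- 7 draws: 12.3%
- 10 draws: 13.8%, which is 1.5 points and a ratio of 1.12 against 7 draws
- 14 draws: 15.2%, which is 2.8 points and a ratio of 1.23 against 7 draws

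For p from 2% to 10%, doubling the draws gives a relative excess of 21% to 25% but only 1.2 to 4.9 points.

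**4. The potassium repeat.** The repeat follows a first value above 5.5 mM, so the share of patients with any such value is the same with or without it. It matters for the stoppage criterion that requires at least two readings, or if each result is counted again. Let h be the share with a first high value, q the share of those that persist, and c the share of such controls who are re-tested. The two-reading rates are h·q on losartan and h·q·c in controls. With h = 10%, q = 50% and c = 50% they are 5.0% and 2.5%, a gap of 2.5 points. With c = 100% there is no gap.

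**The case against.** The strongest reply is that unequal testing is nowhere documented. The Losartan section ties blood work on treatment to clinical indication, Parameters to be collected takes potassium and other values as available in the medical record, and an instruction to monitor for safety orders no test. The sentence on following controls for data only comes directly after the bullet on swabs and research plasma, so it may mean no more than that controls give no research samples. The study schematic, which could hold testing times, was not readable in the text reviewed.

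Most of this stands. A reader might infer that losartan patients have a fixed schedule of safety laboratories while controls have only routine values. The documents do not support that, because they give no laboratory frequency for either group. A reader might also infer that the potassium repeat raises detection of hyperkalemia. It does not: it is worded as a committee suggestion, it needs a high value first, and nothing says that a control with a high value would go untested.

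The reply does not restore like-for-like counting. Table 1 prompts closer follow-up in terms written for people taking losartan, the footnote expects frequent draws, one stoppage item can be met only on treatment, and no readable text sets a common rule for both groups.

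**Conclusion.** The point holds as a gap in the plan: equal AE ascertainment is not ensured, and the safety rule rests on raw totals that are sensitive to it. The evidence supports a plausible bias against losartan, not a demonstrated one.

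Its size cannot be fixed from the documents. It depends on the scale of the margin, the counting unit, the laboratory share of AEs and the within-patient correlation. If every result counts and the margin is relative, 20% to 40% more tests reach 1.20 for a laboratory share between all and half. If patients are counted and the margin is 20 percentage points, even doubling the tests reaches it only with independent draws and a per-draw rate of about 5% or more; at correlation 0.5 it stays below 5 points for the rates examined. A reader might infer that the ±20% rule would fail on testing intensity alone. That is possible under some of these assumptions and is not established.

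The change is worth making: it is cheap, and without it neither a pass nor a failure of the comparison can be read cleanly.

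**What to change.** Add the following to Sample size and Statistics, for the between-group comparison only:

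1. Derive laboratory AEs in every group by the same rule from health-record values, over a common time window. The window needs a start date that does not rely on consent, because AE collection now begins when the consent form is signed and retrospective controls sign none.
2. Use the worst value per analyte per calendar day, excluding repeat draws prompted by the protocol.
3. Count each analyte once per patient, at worst grade.
4. Leave out stoppage items that only a losartan-treated patient can meet.
5. Report tested days per patient by group. Counting once per patient reduces the effect of extra testing but does not remove it (steps 2 and 3 of the working), so this table is needed to judge what remains.
6. Give a rate per tested day as a sensitivity analysis only, with tested days accrued up to the first event. It should not be primary: sicker patients are tested more, and a simple offset does not fit once-per-patient counting.

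Monitoring of losartan patients and the DSMB listings stay as they are.

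The cost is a paragraph of analysis text, a little more data extraction (result dates and times) and a way to identify prompted repeats. The downside is that values seen only on a prompted repeat leave the between-group comparison. They remain in individual safety review and in the DSMB listings.
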